Objective	To evaluate effectiveness and benefits in patients with lower limb impairment in activities of daily living comparing the C-Brace microprocessor – controlled stance and swing orthosis to standard of care use of knee ankle foot orthosis/stance control orthoses
Design	Prospective international multicenter open-labeled randomized controlled cross-over trial
Devices	C-Brace, KAFOs, SCOs
Primary Efficacy End-point	Improvement of static and dynamic balance by using C-Brace compared to KAFO /SCO
Secondary Endpoints	
 1. To evaluate the effect of the C-Brace compared to KAFO/SCO on gait, balance, plain level walking, walking during more challenging tasks and divided attention tasks during walking. 2. To assess and compare the safe use of the C-Brace compared to KAFO/SCO in regards to falls: frequency of falls, severity of falls, fall-related injuries, fear of falling and related treatment efforts. 3. Evaluation of patient`s confidence in performing various ambulatory activities without falling using C-Brace compared to KAFO/SCO. 4. Assessment of quality of life and re-integration to normal living using C-Brace compared to KAFO/SCO. 5. Assessment of disability and impact on productivity. 6. Assessment of patient`s C-Brace satisfaction and usage habits compared to KAFO/SCO 7. Reduced probability of falling more than once by using C-Brace compared to KAFO / SCO

ottobock.	CLINICAL INVESTIGATION PLAN	Document number:	PD-PS00120016A-001
		Version number:	7
Project name	Clinical trial comparing C-Brace to KAFO/SCO	Project no.	PS00120016A

Clinical Follow-up	Screening, 2 baselines, visit 1 after 3 months usage of device 1 at home, visit 2 after 3 months usage of device 2 at home
No of patients	At least 56 randomized
Inclusion criteria	
 • Patient has been tested with the Trial Tool (DTO) and demonstrated the potential to utilize the C-Brace successfully • Patient has a BBS score < 45 • Lower limb functional impairment according to CE label wording • Prior active and compliant use of unilateral or bilateral KAFO or SCO in the past 3 months prior to enrollment in the study • Patient meets minimum physical requirements to be fitted with a C-Brace, such as muscle status, joint mobility, leg axis and proper control of the orthosis must be guaranteed. • The User must fulfill the physical and mental requirements for perceiving optical/acoustic signals and/or mechanical vibrations • The existing muscle strength of the hip extensors and flexors must permit the controlled swing-through of the limb (compensation using the hip is possible). • Patient´s commitment to use C-Brace 2 at least 1-2 hours per day 5 days per week- • Patient is ≥ 18 years old • Patient is willing and able to independently provide informed consent. • Person is willing to comply with study procedures
Exclusion criteria	
 • Patient who is not able to follow the entire study visits or is unwilling/unable to follow the instructions • Patient was not able to use DTO • Patient who is not using an orthosis at least 1 to 2 hours/

ottobock.	CLINICAL INVESTIGATION PLAN	Document number:	PD-PS00120016A-001
		Version number:	7
Project name	Clinical trial comparing C-Brace to KAFO/SCO	Project no.	PS00120016A

	
day for 5 days per week
 
 • Patient with body weight > 125 kg (includes body weight and heaviest object (weight) carried) • Patient with Orthoprosthesis • Patient with flexion contracture in the knee and/or hip joint in excess of 10° • Patient with uncontrolled moderate to severe spasticity (relative contraindication moderate spasticity) • Leg length discrepancy in excess of 15 cm • Patient with unstable neurological or cardiovascular/pulmonary disease, cancer • Pregnancy • Patient using a C-Brace • Patient with known vertigo or with history of falls unrelated to orthosis use or unrelated to motor disability • Patient who has never been fitted an orthosis before • Patient is not able to answer the self-administered questionnaires independently; for patients with upper extremity impairment is it allowed to verbally answer the questions. • Patient participating already in a study during this study's duration • Patient participated in earlier C-Brace studies
Estimated Time Course	
Estimated study duration:
 
First Patient In: 1 Mar 2019
 
Last Patient In: 31 Dec 2021
 
Last Patient Out: 31 Mar 2023

Principal Investigators	
Site 1: [name]
 
Site 2: [name]
 
Site 3: [name]
 
Site 4: PD [name]

ottobock.	CLINICAL INVESTIGATION PLAN	Document number:	PD-PS00120016A-001
		Version number:	7
Project name	Clinical trial comparing C-Brace to KAFO/SCO	Project no.	PS00120016A

	
Site 5: [name], CPO, FAAOP
 
Site 6: [name], LO, CO, FAAOP
 
Site 7: [name], LCO, ACM
 
Site 8: [name], LCPO, FAAOP
 
Site 9: [name]

Clinical Site Locations	
Site 1: Göttingen (D)
 
Site 2: Koblenz (D)
 
Site 3: Hoensbroek (NL)
 
Site 4: Heidelberg (D)
 
Site 5: Chicago, IL (USA)
 
Site 6: Houston, TX (USA)
 
Site 7: Sarasota, FL (USA)
 
Site 8: Seattle, WA (USA)
 
Site 9: Wien (AT)

Clinical Project Manager	[name]

ottobock.	CLINICAL INVESTIGATION PLAN	Document number:	PD-PS00120016A-001
		Version number:	7
Project name	Clinical trial comparing C-Brace to KAFO/SCO	Project no.	PS00120016A

2 Abbreviations

AE	Adverse Event
ABC	Activities-specific balance confidence scale
ADE	Adverse Device Effect
BBS	Berg Balance Scale
C-Brace	Axon Orthotic System
CRF	Case Report Form
CB2	C-Brace 2 (the New C-Brace)
CIP	Clinical Investigation Plan = Protocol
CPO	Certified Prosthetist/Orthotist
DGI	Dynamic Gait Index
DTO	Trial tool (Diagnostische Testorthese)
EC	Ethics Committee
GCP	Good Clinical Practice
ICF	Informed Consent Form
KAFO	Knee Ankle Foot Orthoses
PRO	Patient reported outcome
OPUS	Orthotic and Prosthetic User Survey
QUEST	Quebec User Evaluation of Satisfaction with Assistive Technology
RNL	Re-integration to normal living
SAE	Serious Adverse Event
SADE	Serious Adverse Device Effect
SAI	Stair Assessment Index
SCO	Stance Control Orthoses
SF-36	Medical Outcome Study Short Form
tdb	To be defined
WLQ	Work limitations questionnaires
US	United States
6MWT	6-Minute Walk Test

ottobock.	CLINICAL INVESTIGATION PLAN	Document number:	PD-PS00120016A-001
		Version number:	7
Project name	Clinical trial comparing C-Brace to KAFO/SCO	Project no.	PS00120016A

3 Background

The estimated incidence for people with lower limb weakness due to neurologic, neuromuscular or orthopedic impairment, such as lower motor neuron injury, spinal cord injury, multiple sclerosis, post-polio syndrome, stroke, arthritis or trauma requiring the use of an orthosis for walking is about 394.400 cases in Germany (1). It is estimated that approximately 0.01 % of those requiring an orthosis will benefit from a C-Brace. Distribution is comparable in other countries like the US.

People with lower limb weakness due to neurologic, neuromuscular or orthopedic impairment, such as lower motor neuron injury, spinal cord injury, multiple sclerosis, post-polio syndrome, stroke, arthritis or trauma may require the use of a knee-ankle-foot orthoses (KAFO) for walking. The conventional KAFO has a knee joint that can be “locked” in extension during ambulation, but this can cause abnormal gait patterns with hip hiking, circumduction and vaulting during walking (2). These gait deviations using conventional KAFOs may contribute to chronic pain, decreased mobility and a higher physiological energy cost (2,3)

Stance Control Orthoses (SCO) are usually knee ankle foot orthoses (KAFO) that have a built-in locking mechanism which locks the knee joint for the stance phase and unlocks it for the swing phase of gait. The stance-control knee-ankle-foot orthosis (SCO) has addressed some of these issues by mechanically locking the orthotic knee joint during the stance phase of gait while allowing free knee flexion during swing.

These devices have been shown to improve gait kinematics and gait speed on level ground in compared to the use of KAFOs (2,4). Due to the method needed to engage the knee lock for stance, however, users have reported increased mental effort to use these devices, specifically to disengage the knee for initiation of swing (5). Success in using SCOs has been limited by balancing the need to resist flexion in stance and providing a lightweight and small device. The challenges that remain for the SCO are to control the knee in flexion, missing knee flexion under load and extension phases and to switch smoothly between the phases (6).

Current evidence finds that the benefit of KAFO use is for home mobility, general exercise and standing (7) and that, in general, most patients feel that the difficulties and inconvenience encountered with the orthoses and the modest increase in function do not warrant their acceptance for regular, daily use in functional activities (7). However, walking provides exercise to promote musculoskeletal and mental health benefits to counteract the effects of long-term wheelchair use. It may also increase functional independence, community participation and re-integration back to normal life and work.

ottobock.	CLINICAL INVESTIGATION PLAN	Document number:	PD-PS00120016A-001
		Version number:	7
Project name	Clinical trial comparing C-Brace to KAFO/SCO	Project no.	PS00120016A

On the other hand, there is low knowledge about disability and the impact on work background as well as re-integration into work.

A KAFO orthotic device that can provide mechanical support while allowing greater control in swing and stance phases of gait may increase the user's ability to walk with decreased metabolic cost and mental effort to allow increase functional mobility and participation in daily activities allowing a self-administered life.

The C-Brace orthotic system is designed with custom thigh and calf shells connected by a monocentric knee joint with a microprocessor-controlled linear hydraulic damper. The orthotic knee is equipped with a sensor that detects the knee angle and knee angle velocity. The microprocessor controls extension and flexion dampening of the hydraulic knee joint separately by adjusting two valves with the help of servomotors and a planetary gear set. In this way, the entire gait cycle is controlled in real time. The C-Brace is a default-stance orthosis that switches into low flexion resistance for swing when a pre-set, customizable ankle moment is exceeded, while the knee is simultaneously extended, followed by significant knee flexion. It switches back to high flexion resistance for stance as early at the initiation of knee extension. The C-Brace offers controlled stance knee flexion, knee flexion during weight-bearing and dynamic control of the swing phase. Knee flexion during weight bearing makes it possible to reciprocally descend ramps and stairs and to sit down with both legs loaded. We hypothesize that the use of C Brace in comparison to conventional KAFO / SCO systems shall lead to a better balance associated with a reduced risk of falling, hence allowing better participation and an increase in quality of life.

C-Brace Clinical data

Title	Objective(s)	Comparator(s)	Patient number	Published
Prospective, pilot study to evaluate performance, patient benefits and acceptance of a new generation of C-Brace microprocessor-controlled stance and swing control orthosis– AOS	Safety and functionality of CB2	KAFO/SCO	8	Study final Dec 2018
Clinical Algorithm for Post-Stroke Gait Training with C-Brace	functionality	N/A	15	recruiting
Micro-processor controlled Knee-Ankle-	Metabolic, functionality, safety	SCO	18	Study final, publication

ottobock.	CLINICAL INVESTIGATION PLAN	Document number:	PD-PS00120016A-001
		Version number:	7
Project name	Clinical trial comparing C-Brace to KAFO/SCO	Project no.	PS00120016A

Foot Orthosis (C-Brace) vs. Stance-control Knee-Ankle-Foot Orthosis (SCO) and conventional Knee-Ankle-Foot Orthosis (KAFO): Functional Outcomes in Individuals with Lower Extremity Impairments due to Neurologic or Neuromuscular Disease, Orthopedic Disease or Trauma (RIC)				in preparation
A Prospective Registry of patients fitted with a microprocessor-controlled knee ankle foot orthosis	Functionality, safety	KAFO/SCO	150	recruiting

Table 1: Published and non-published clinical data on C-Brace

4 Rationale

The C-Brace microprocessor (MP) controlled hydraulic system is the next generation in the development of lower limb orthoses allowing more control during the swing and stance phases of gait. The device will provide better static and dynamic balance leading to a reduced risk of falling. Improvements may comprise stand to sit transfers, walking on uneven surfaces, slopes and stairs. Such functions may help to improve patients' mobility, integration, participation and quality of life.

The study will specifically evaluate the potential of the C-Brace to improve the efficacy in daily life activities and benefits for individuals with lower extremity functional impairments as compared to SCOs and conventional KAFOs.

5 Investigational Device Information

Intervention: C-Brace

5.1 Manufacturer

Otto Bock Healthcare Products GmbH
[name],
[name]

Otto Bock

Confidential

Page 25 of 89

ottobock.	CLINICAL INVESTIGATION PLAN	Document number:	PD-PS00120016A-001
		Version number:	7
Project name	Clinical trial comparing C-Brace to KAFO/SCO	Project no.	PS00120016A

Austria

Version investigational device

Model number: 17KO1=*

Device name: 17KO1 C-Brace Gelenkeinheit / C-Brace joint unit

Investigational device comprises:

- Microprocessor controlled knee joint (model no. 17KO1)
- Custom made orthotic shells for each patient

C-Brace is a class I device according to 93/42/EEC Annex IX and according to Regulation (EU) 2017/745 Annex VIII

CE-mark was obtained 14 Jun 2018.

For further technical details about the product, product development and testing procedures please refer to the Investigator's brochure (IB).

5.2 Description of the investigational device

Intended use

The C-Brace microprocessor swing and stance control orthosis is used for patients with paresis or flaccid paralysis of the lower limbs (e.g. due to post-polio syndrome, traumatic paresis including paraplegia) requiring orthotic knee support.

Indications / Contraindications C-Brace

Suitable patients will fulfil the following criteria:

- Unilateral or bilateral lower limb paresis or flaccid paralysis e.g. due to post-polio syndrome, traumatic paresis including paraplegia.
- Physical prerequisites such as muscle status, joint mobility and possible axis deviations are crucial and proper control of the orthosis must be guaranteed.
- The user must fulfill the physical and mental requirements for perceiving optical/acoustic signals and/or mechanical vibrations
- The existing muscle strength of the hip extensors and flexors must permit the controlled swing through of the limb (compensation using the hip is possible).

Patients will not be suitable for using the system if they show the following:

Absolute contraindications:

- Flexion contracture in the knee and/or hip joint in excess of 10°
- Knee varus/valgus malposition in excess of 10°
- Severe spasticity

ottobock.	CLINICAL INVESTIGATION PLAN	Document number:	PD-PS00120016A-001
		Version number:	7
Project name	Clinical trial comparing C-Brace to KAFO/SCO	Project no.	PS00120016A

- Body weight over 125 kg / 275 IBs

Relative Contraindications

- Moderate spasticity

Technical description of the C-Brace

The C-Brace consists of individually manufactured orthotic shells, which interface with the thigh, shank and foot. The orthotic shells are made out of commonly used materials in orthotics.

The knee joint is controlled by a microprocessor controlled joint unit, while the ankle joint is designed according to the patient's needs. Elastic elements (such as the C-Brace carbon fiber spring) or state of the art orthotic joints can be used.

Figure 1 C-Brace existing of thigh, tibial and foot shell, mpKnee joint and medial follower.

Knee joint motion is controlled using a microprocessor-controlled joint (mpKnee joint) which consists of microprocessor-controlled hydraulic cylinders that can provide variable resistance. The microprocessor uses the signals from various sensors to adjust the joint behavior in real-time, according to situation (i.e. phase in gait cycle). For example, during stance phase of gait the knee joint provides high resistance to stabilize the patient. During swing phase, the knee joint switches to minimum resistance and is almost free (only inner friction of the system). At maximum resistance, joint motion is blocked. The joints are capable of providing any resistance between these extreme points. For further technical details about the mpKnee joint unit, please refer to chapter 5.2.1 Technical description of mpKnee Joint.

The patient has the possibility to turn the system on and off via a control panel. Furthermore, the patient gets information on the control panel about the battery status, if service is required (after a certain amount of cycles or if a problem with the sensor is

ottobock.	CLINICAL INVESTIGATION PLAN	Document number:	PD-PS00120016A-001
		Version number:	7
Project name	Clinical trial comparing C-Brace to KAFO/SCO	Project no.	PS00120016A

detected by the system) and about the Bluetooth status (see Figure 2: Control panel of C-Brace). Bluetooth can be initialized by the patient if he/she wants to use the Remote Control App. The App will be comparable to the one available for Ottobock's microprocessor controlled prosthetic knee and foot prostheses Genium, C-Leg and Meridium. The use and application of the control panel as well as the Remote Control App is described more detailed in the instruction for use.

[figure not shown]

Figure 2: Control panel of C-Brace

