9.3.1 Inclusion criteria

- Patient has been tested with the Trial Tool (DTO) and demonstrated the potential to utilize the C-Brace successfully (see section benchmarks: independent donning/doffing of the orthosis, charging of the device, transfers sit to stand/stand to sit, standing in the orthosis with or without assisted device for a minimum of 2 minutes, safe over ground ambulation, ambulatory turns and to perform a swing phase).
- Patient has a BBS score < 45
- Lower limb functional impairment according to CE label wording
- Prior active and compliant use of unilateral or bilateral KAFO or SCO in the past 3 months prior to enrollment in the study
- Patient meets minimum physical requirements to be fitted with a C-Brace, such as muscle status, joint mobility, leg axis and proper control of the orthosis must be guaranteed.

ottobock.	CLINICAL INVESTIGATION PLAN	Document number:	PD-PS00120016A-001
		Version number:	7
Project name	Clinical trial comparing C-Brace to KAFO/SCO	Project no.	PS00120016A

- The User must fulfill the physical and mental requirements for perceiving optical/acoustic signals and/or mechanical vibrations
- The existing muscle strength of the hip extensors and flexors must permit the controlled swing-through of the limb (compensation using the hip is possible).
- Patient's commitment to use C-Brace 2 at least 1-2 hours per day 5 days per week-
- Patient is ≥ 18 years old
- Patient is willing and able to independently provide informed consent.
- Person is willing to comply with study procedures

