9.3.2 Exclusion criteria

- Patient who is not able to follow the entire study visits or is unwilling/unable to follow the instructions
- Patient was not able to use DTO
- Patient who is not using an orthosis at least 1 to 2 hours/ day for 5 days per week
- Patient with body weight > 125 kg (includes body weight and heaviest object (weight) carried)
- Patient with Orthoprosthesis
- Patient with flexion contracture in the knee and/or hip joint in excess of 10°
- Patient with uncontrolled moderate to severe spasticity (relative contraindication moderate spasticity)
- Leg length discrepancy in excess of 15 cm
- Patient with unstable neurological or cardiovascular/pulmonary disease, cancer
- Pregnancy
- Patient using a C-Brace
- Patient with known vertigo or with history of falls unrelated to orthosis use or unrelated to motor disability
- Patient who has never been fitted an orthosis before
- Patient is not able to answer the self-administered questionnaires independently; for patients with upper extremity impairment is it allowed to verbally answer the questions.
- Patient participating already in a clinical study during this study's duration
- Patient participated in earlier C-Brace studies

Additional determination of exclusion criteria for Austrian centers:

Pregnant and nursing women are NOT allowed to participate in this study.

Women of childbearing age are only allowed to participate in this study, if they have confirmed that they are not pregnant before the study (according to a pregnancy test). They will be asked to perform pregnancy tests once a month during the study. Female patients will be asked to inform the investi-

ottobock.	CLINICAL INVESTIGATION PLAN	Document number:	PD-PS00120016A-001
		Version number:	7
Project name	Clinical trial comparing C-Brace to KAFO/SCO	Project no.	PS00120016A

gator immediately, if they become pregnant during the study, or suspect that they are pregnant. Their participation in the study will be terminated under these circumstances.

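### Of the four absolute contraindications in Section 5.2, one is missing from every exclusion list and one appears only in a narrowed or ambiguous form

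*Combined protocol and SAP*

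**What the plan says.** Section 5.2 names four findings that make a patient unsuitable for the device in absolute terms:

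- "Flexion contracture in the knee and/or hip joint in excess of 10" degrees
- "Knee varus/valgus malposition in excess of 10" degrees
- "Severe spasticity"
- "Body weight over 125 kg / 275 IBs"

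Moderate spasticity is listed there separately, as the only relative contraindication.

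Section 9.3 decides who may be registered: every inclusion criterion must be met and no exclusion criterion may be. Three exclusions in 9.3.2 correspond to the list in 5.2:

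- "Patient with flexion contracture in the knee and/or hip joint in excess of 10" degrees
- "Patient with body weight > 125 kg (includes body weight and heaviest object (weight) carried"
- "Patient with uncontrolled moderate to severe spasticity (relative contraindication moderate spasticity"

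The exclusion lists in Section 1 and in the German overview (23.2) have the same three items. None of the three lists has a varus/valgus item.

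Among the inclusion criteria, 9.3.1 has "Patient meets minimum physical requirements to be fitted with a C-Brace, such as muscle status, joint mobility, leg axis". It attaches no angle to leg axis. Another inclusion criterion ties the limb impairment to the CE label. No inclusion criterion mentions spasticity.

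**The concern.** The part of the protocol that says who must not wear the device and the part that says who may enter the trial do not match. Section 9.3 governs registration, so a difference there counts more than one in descriptive text. A patient whom 5.2 calls unsuitable could satisfy the eligibility lists and be randomised, and in this crossover every patient is meant to use the C-Brace in one of the two periods.

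Safety comes first. There is also a matter of interpretation. Section 15.2 defines a major deviation partly as non-adherence to the inclusion or exclusion criteria, and 10.3 removes patients with major deviations from the per-protocol population. A contraindicated patient who meets the lists as written has not breached them, so on eligibility grounds would stay in that population. Falls are a secondary outcome, the recruitment target of 56 rests on the probability of falling more than once (10.1.2), and 16.2 gives many reported falls as a reason to end the study. Who is eligible should therefore be unambiguous.

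**Working it through.** No arithmetic beyond a count applies, so the check is an item-by-item comparison of 5.2 with the eligibility lists.

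| Absolute contraindication in 5.2 | Exclusion lists (Section 1, 9.3.2, 23.2) | Inclusion criteria (9.3.1) | Result |
|---|---|---|---|
| Flexion contracture above 10° | Present, same limit | Joint mobility named in general terms | Carried over |
| Body weight over 125 kg | Present, and stricter because carried load counts | Not named | Carried over |
| Varus/valgus above 10° | Absent from all three | Leg axis named, no limit | Omitted |
| Severe spasticity, unqualified | Present with the qualifier uncontrolled | Not named | Narrowed or ambiguous |

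The count is 2 carried over + 1 omitted + 1 narrowed or ambiguous = 4.

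**Spasticity.** The exclusion can be read in two ways.

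1. If uncontrolled governs both grades, the exclusion covers uncontrolled moderate and uncontrolled severe spasticity. Severe but controlled spasticity is then not excluded, which contradicts 5.2.
2. If uncontrolled governs only the moderate grade, all severe spasticity is excluded and the text agrees with 5.2.

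The plan does not say which reading is meant. The German wording repeats the same qualifier and range, so it does not settle the matter.

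**Varus/valgus.** Could other text supply the missing limit?

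- *Leg-axis inclusion criterion.* It echoes the general suitability statement in 5.2, which also mentions axis deviations. But 5.2 gives that general statement and, separately, the 10° limit, so it does not let one stand in for the other. The same inclusion criterion names joint mobility, yet flexion contracture still has its own numerical exclusion. Varus/valgus is the one angular limit in 5.2 left without one.
- *CE-label inclusion criterion.* It describes the impairment. The German overview renders it as the indication in the instructions for use, so it points to indications and not to contraindications.
- *Screening tests (7.3.2.1).* They include muscle, sensitivity and passive range-of-motion tests. Neither a leg-axis measurement nor a spasticity grading is named.
- *DTO test (7.3.2.4, 9.3.1).* It checks donning, transfers, standing, walking, turning and producing a swing phase. It includes no angle and no spasticity grade.
- *Level 1 benchmark (7.3.4.3).* This too is a list of functional tasks, and it comes after randomisation.

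A patient with varus/valgus above 10° therefore meets no listed exclusion and is stopped only if an investigator judges the leg axis inadequate or the patient fails a functional test. Under the first reading, a patient with controlled severe spasticity meets no listed exclusion, and no inclusion criterion addresses the condition by name.

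**The case against.** The best reply is that passing the exclusions is not the same as being eligible. The leg-axis criterion must also be met, and an investigator applying it would naturally look to the 10° figure elsewhere in the same protocol. Fitting must follow the manufacturer's instructions, the technician must be certified, and the eligibility checklist, instructions for use and Investigator's Brochure, which are not available here, may state the limits. On spasticity, the bracketed note in the exclusion repeats the relative contraindication from 5.2, which suggests that 5.2 was meant to be carried over.

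Much of this stands. For varus/valgus a check exists and only its limit is missing; the spasticity conflict depends on how one phrase is parsed. It does not remove the point. Judgement without a stated limit can differ across the nine listed sites, the functional tests apply neither 5.2 limit, and an ambiguity about an absolute contraindication itself needs resolving.

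Two stronger readings are tempting, and the documents do not support them.

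- *That two contraindications are simply missing.* Severe spasticity is in the exclusion lists; the qualifier narrows it or makes it unclear. Only varus/valgus is wholly absent.
- *That a contraindicated patient would be obliged to use the device at home for 3 months.* The DTO test comes before enrolment. Home use requires the Level 1 benchmark, shown at two points in time (7.3.4.2, 7.3.4.3), and discharge requires safe walking (5.3.2). The patient may withdraw, and the investigator may end participation, at any time (9.3.3).

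**Conclusion.** The point holds: the plan is wrong as written, because 5.2 and the eligibility lists contradict each other on varus/valgus and, on one natural reading, on severe spasticity. The extent is two of four absolute contraindications, one omitted and one narrowed or ambiguous.

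A reader might infer a measurable excess of falls or poor fittings, or a distorted Berg Balance Scale result. The documents do not support that. They give no frequency for either condition among existing KAFO/SCO users, so the number of patients affected cannot be derived, and no effect on the primary analysis can be shown.

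The conclusion rests on two assumptions: that sites apply the lists in 9.3 as written, and that no unseen site document supplies the limits. Such a document could reduce the practical risk, but the protocol would still contradict itself. The statement about deviations is confined to eligibility grounds, because 15.2 also allows a deviation to be classed as major for its effect on patient safety. This should be corrected, but it does not call the trial design into question.

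**What to change.** Reconcile Section 5.2, the inclusion criteria in 9.3.1 and the exclusion criteria in 9.3.2 with the English synopsis (Section 1) and the German overview (23.2), so that the varus/valgus and spasticity statements agree everywhere. For spasticity, the agreed text should leave no doubt about which grades the word uncontrolled governs. Which clinical wording applies is for the sponsor to decide with the investigators; this review proposes none. Any eligibility checklist should then follow the agreed text.

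The cost is a wording amendment, with the review that amendments require under 15.3, and possibly a few more screening failures. No sample size or analysis text has to change.
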